#### 6.3.1.1 Pyrexia

Episodes of pyrexia syndrome have been observed in patients receiving dabrafenib monotherapy or in combination with trametinib. The pyrexia syndrome is defined as treatment-related fever (≥38°C) or chills/rigors/night sweats or flu-like symptoms. In a minority of cases pyrexia was accompanied by symptoms such as severe chills/rigors, dehydration, and hypotension, dizziness or weakness and required hospitalization. The incidence and severity of pyrexia syndrome are increased when dabrafenib is used in combination with trametinib compared to dabrafenib monotherapy.

Patients and guardians must be instructed on the importance of immediately reporting febrile episodes. Dabrafenib and trametinib must be interrupted promptly and anti-pyretics (acetominophen, ibuprofen, similar) started at the very first symptom of pyrexia or its associated prodrome (chills or rigors or night sweats or flu-like symptoms). Adequate hydration status should be maintained. Dabrafenib and trametinib should be restarted upon improvement of symptoms of at least 24 hours, and at the same dose.

In the event of recurring pyrexia events despite the use of antipyretics and drug interruption, the use of oral corticosteroids may be considered when restarting dabrafenib and trametinib. In patients experiencing pyrexia associated with rigors, severe chills, dehydration or hypotension, serum creatinine increase and other evidence of renal function decrease should be monitored carefully during and following severe events of pyrexia.

Pyrexia accompanied by hypotension, dehydration requiring intravenous fluids, renal insufficiency and/or severe (≥ Grade 3) rigors/chills in the absence of an obvious infectious cause are to be reported as a SAE.

Guidelines for dose modification and management for pyrexia syndrome considered to be related to dabrafenib are provided in Table 6-16.

Table 6-16 Mandatory dose modification and recommended clinical management for pyrexia syndrome suspected to be related to dabrafenib and/or trametinib treatment

| Pyrexia   |   |   |  |
|---|---|---|--|
| Occurrence  | Recommended adverse event management guidelines   | Mandatory dose modification requirements  |  |
| 1 st occurrence and
subsequent
occurrence s | 
 
Re-educate patient/family about pyrexia syndrome and immediately interrupt dabrafenib and trametinib at the very first symptom of pyrexia or its associated prodrome (chills or rigors or night sweats or flu-like symptoms).
 
Clinical evaluation for infection and hypersensitivitya
 
Laboratory work-upa
 
Administer anti-pyretic treatment with nonsteroidal anti-inflammatory drugs (NSAID) and/or paracetamolb
 
Oral hydration should be encouraged in patients without evidence of dehydration. Intravenous hydration is recommended in patients experiencing pyrexia complicated by dehydration/hypotension.
 
For recurring pyrexia events despite the use of anti-pyretics and dose interruption, consider oral corticosteroids (i.e. prednisone 10mg or pediatric equivalent, or more) for at least 5 days or as clinically indicated.
 
Optimize oral corticosteroid dose as clinically indicated for recalcitrant pyrexia
 
 | Dabrafenib and trametinib must be interrupted promptly at the very first symptom of pyrexia or its associated prodrome (chills, rigors, night sweats or flu-like symptoms) Adequate hydration status should be maintained. Dabrafenib and trametinib should be restarted upon improvement of symptoms of at least 24 hours, at the same dose     If pyrexia cannot be managed with interruption, dose reduction must be considered if clinically indicated. |  |

- a. For patients experiencing pyrexia, a clinical evaluation and laboratory work-up is mandatory for each event; thorough clinical examination for signs and symptoms of infection or hypersensitivity is required; laboratory work-up should include full-blood-count, electrolytes, creatinine, blood urea nitrogen (BUN), Creactive protein (CRP), liver transaminases, blood culture, and urine culture.
- b. Anti- pyretic treatment should be started immediately at the first occurrence and prophylactic anti-pyretic treatment is recommended. Anti-pyretic treatment may include acetaminophen, ibuprofen, or suitable anti-pyretic medication according to institutional standards. Prophylactic anti-pyretic treatment is recommended to be discontinued after three days in the absence of pyrexia.

#### 6.3.1.2 Renal Insufficiency

Cases of renal insufficiency have occurred in adult patients receiving dabrafenib and the combination of dabrafenib and trametinib. Prior to start of study treatment, concomitant medications must be reviewed for the potential risk of inducing nephrotoxicity and concomitant medications may be modified if clinically possible.

Guidelines regarding management and dose reduction for renal insufficiency considered to be related to study treatment by the investigator are provided Table 6-17.

Table 6-17 Mandatory dose modifications and recommended clinical management guidelines for renal function alterations

| NCI-CTCAE v4.03                          |  |  |
|--|--|--|
| Grade                                    | Recommended adverse event
management guidelines   | Mandatory dose modification requirements   |
| Grade 1 (Creatinine > ULN to ≤ 1.5× ULN) | 
 
Monitor creatinine weekly
 
If creatinine return to baseline resume routine creatinine monitoring per protocol
 
Promote hydration and cessation of nephrotoxic drugs.
 
 | Continue dabrafenib and trametinib at the same dose.   |
| Grade 2 (Creatinine > 1.5× to ≤ 3× ULN   | 
 
Monitor creatinine every 2 to 3 days
 
Consult with specialist and consider renal biopsy
 
Promote hydration and cessation of nephrotoxic drugs.
 
                       | 
 
Interrupt dabrafenib and trametinib until ≤ Grade 1 or baseline and then reinstate dabrafenib and trametinib at the same dose.
 
2nd occurrence:         
 
Interrupt dabrafenib and trametinib until ≤ Grade 1 or baseline. Once recovered, reduce dabrafenib and trametinib to the next dose level. Re-escalation of the patient's dose is recommended if criteria in Section 6.3.1 are met.
 
 
 
3rd occurrence:         
 
Interrupt dabrafenib and trametinib until ≤ Grade 1 or baseline. Once recovered, reduce dabrafenib and trametinib to the next dose level. Re-escalation of the patient's dose is recommended if criteria in Section 6.3.1 are met.
 
 
 
4th occurrence         
 
Permanently discontinue dabrafenib and trametinib.
 
 
 
 |
| Grade 3 (Creatinine > 3.0 to < 6×ULN)    | 
 
Monitor creatinine every 1 to 2 days.
 
Consult with nephrologist.
 
Promote hydration and cessation of nephrotoxic drugs.
 
   | 
 
1st occurrence:
 
Interrupt dabrafenib and trametinib until ≤ Grade 1 or baseline and then reduce dabrafenib and trametinib to the next lower. Re-escalation of the
 
   |

Protocol No. CDRB436G2201

| Grade                        | Recommended adverse event management guidelines   | Mandatory dose modification requirements   |
|------------------------------|---|--|
|                              |   | patient's dose is recommended if criteria in Section 6.3.1 are met.  |
|                              |   | 2 nd occurrence:  |
|                              |   | 
 
Interrupt dabrafenib and
trametinib until ≤ Grade 1 or
baseline and then reduce
dabrafenib and trametinib to the
next lower dose. Re-escalation of
the subject's dose is
recommended if criteria in Section
6.3.1 are met.
 
   |
|                              |   | 3 rd occurrence:  |
|                              |   | Interrupt dabrafenib and trametinib until ≤ Grade 1 or baseline and then reduce dabrafenib and trametinib to the next lower dose, if available as dose level -2. If already at dose level -2 at time of occurrence, permanently discontinue dabrafenib and trametinib. Reescalation of the patient's dose is recommended if criteria in Section 6.3.1 are met. |
|                              |   | 4 th occurrence:  |
|                              |   | 
 
Permanently discontinue
dabrafenib and trametinib.
 
   |
| Grade 4: Creatinine > 6× ULN | 

Monitor creatinine daily.

Consult with specialist and recommend renal biopsy.

 | 
 
Permanently discontinue
dabrafenib and trametinib.
 
   |
|                              | Promote hydration and cessation of nephrotoxic drugs.   |  |

#### 6.3.1.3 Pneumonitis

Pneumonitis has been observed in patients receiving trametinib in combination with dabrafenib. Guidelines for dose modification and management of pneumonitis considered to be related to study treatment by the investigator are provided in Table 6-18.

Table 6-18 Mandatory dose modifications and recommended clinical management guidelines for pneumonitis

| Pneumonitis (NCI-CTCAE   | Ev4.03)   |   |
|--|---|---|
| Grade  | Recommended adverse event management guidelines   | Mandatory dose modification requirements  |
| Grade 1: Radiographic changes only-
Asymptomatic  | 
 
CT scan (high-resolution with lung windows) recommended, with serial imaging to monitor for resolution or progression- reimage at least every 3 weeks
 
Monitor for symptoms every 2-3 days - Clinical evaluation and laboratory work-up for infection
 
Monitoring of oxygenation via pulse oximetry recommended
 
Consultation of pulmonologist recommended.
 
   | Continue dabrafenib and trametinib at the same dose.  |
| Grade 2: Symptomatic medical intervention indicated; limits instrumental Activities of Daily Living (ADLs) | 
 
CT scan (high-resolution with lung windows)
 
Monitor symptoms daily, consider hospitalization
 
Clinical evaluation and laboratory work up for infection
 
Consult pulmonologist
 
Pulmonary function tests if normal at baseline, repeat every 8 weeks
 
Bronchoscopy with biopsy and/or bronchoscopic alveolar lavage (BAL) recommended
 
Symptomatic therapy including corticosteroids if clinically indicated (systemic corticosteroids at a dose of 1 to 2 mg/kg/day prednisone or equivalent as clinically indicated).
 
 | 
 
1st occurrence:         
 
Interrupt trametinib until recovery to ≤ Grade 1 or baseline. Dabrafenib may continue at the same dose.
 
Once recovered, reduce trametinib to the next lower dose. Re-escalation of the patient's dose is recommended if criteria in Section 6.3.1 are met.
 
If no recovery to ≤ Grade 1 within 4 weeks, permanently discontinue trametinib. Dabrafenib may continue.
 
If worsens treat as Grade 3 or 4.
 
 
 
 |
| Grade 3: Severe symptoms; limits self-care ADLs; oxygen indicated  | 
 
CT scan (high-resolution with lung windows)
 
Clinical evaluation and laboratory work-up for infection
 
Consult pulmonologist
 
Pulmonary function tests-if < normal, repeat every 8 weeks until ≥ normal
 
Bronchoscopy with biopsy and/or BAL if possible
 
Treat with intravenous steroids (methylprednisolone 125 mg or equivalent) as indicated. When symptoms improve to ≤ Grade 1, a high dose oral steroid (prednisone 1 to 2 mg/kg/day or dexamethasone 4 mg every 4 hours or equivalent).
 
                              | 
 
Interrupt trametinib until recovery to Grade ≤1 or baseline. Dabrafenib may continue.
 
Once recovered, trametinib may be restarted at the next lower dose. Re-escalation of the patient's dose is recommended if criteria in Section 6.3.1 are met.
 
If no recovery to Grade ≤ 1 or baseline within 4 weeks, permanently discontinue trametinib. Dabrafenib may continue.
 
   |

| Pneumonitis (NCI-CTCAE v4.03)                  |   |  |  |
|--|---|--|--|
| Grade  | Recommended adverse event management guidelines   | Mandatory dose modification requirements |  |
|  | If IV steroids followed by high
dose oral steroids does not
reduce initial symptoms within
48 to 72 hours, consider non-
corticosteroid
immunosuppressive medication |  |  |
| Grade 4: Life- threaten respiratory compromise |   | Same as Grade 3                          |  |

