#### 5.2 Inclusion criteria

Patients eligible for inclusion in this study have to meet all of the following criteria:

- 1. Male or female between ≥12 months and <18 years of age at the time of signing the informed consent form. Patients under 6 years old must weigh at least 7 kg at the time of enrollment. Patients over 6 years old must weigh at least 10 kg at the time of enrollment.
- 2. **For HGG cohort only:** Relapsed, progressed, or failed to respond to frontline therapy. Frontline therapy is presumed to be optimal surgical approach (biopsy or resection) with radiation and/or chemotherapy.
  - **For LGG cohort only:** Patients with progressive disease following surgical excision, or non-surgical candidates with necessity to begin first systemic treatment because of a risk of neurological impairment with progression.
- 3. Locally determined HGG or LGG as defined by WHO histological classification system, revised 2016 (Appendix 4). For HGG cohort only: Locally confirmed histologic diagnosis of High Grade Glioma (Grade III or IV glioma), including anaplastic pleomorphic xanthoastrocytoma (aPXA) and anaplastic gangliogliomas.
  - **For LGG cohort only**: Locally confirmed histologic diagnosis of Low Grade Glioma (Grade I or II)
- 4. Locally determined and centrally confirmed measurable disease with minimal biperpendicular diameter that must be at least twice the imaging slice thickness to be used for efficacy assessments. (Both local and centrally confirmed results must show measurable disease to meet eligibility)
- 5. *BRAF* V600 mutation-positive tumor as assessed locally, or at a Novartis designated central reference laboratory if local *BRAF* V600 testing is unavailable.
- 6. Tumor tissue must be available and subsequently provided to Novartis for central confirmatory testing of *BRAF* mutational status (HGG and LGG cohort), and for HGG histopathology (HGG cohort).
- 7. Performance score of  $\geq$ 50% according to the Karnofsky/Lansky performance status scale.
- 8. Females of child-bearing potential must be willing to practice acceptable methods of birth control. Additionally, females of childbearing potential must have a negative serum pregnancy test within 28 days prior to day 1.
- 9. Must have adequate bone marrow function per central or local lab in the absence of growth factor support and is defined as:
  - Absolute neutrophil count (ANC) ≥1000/μL;

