#### 6.1.1.1 Dabrafenib (DRB436) and trametinib (TMT212) dosing

Study medications should be taken as follows:

- Dabrafenib will be administered twice daily per the dosing regimen shown in Table 6-1, Table 6-2, Table 6-3 and Table 6-4.
- Trametinib will be administered once daily per the dosing regimen shown in Table 6-5, Table 6-6, Table 6-7 and Table 6-8.
- Trametinib should be taken in combination with dabrafenib once daily, preferably in the morning.
- Dabrafenib capsules and trametinib tablets should be taken with approximately 120-240 mL of water.
- Trametinib pediatric oral solution formulation will be administered with a graduated syringe. Please refer to the trametinib oral solution Instructions for Use.
- Dabrafenib pediatric oral suspension formulation administration will be administered using dosing cup and/or graduated syringe. Please refer to dabrafenib oral suspension Instructions for Use.
- Refer to the dabrafenib and trametinib Instructions for Use documents if enteral feeding tubes are required for administering pediatric oral solutions.
- Patients less than 12 years of age who weigh less than 16 kg must be administered the dabrafenib dispersible tablets for oral suspension.
- Patients equal to or greater than 12 years of age who weigh less than 19 kg must be administered the dabrafenib dispersible tablets for oral suspension.
- Patients less than 6 years old who weigh less than 26 kg must be administered the trametinib oral solution.
- Patients older than 6 years old must weigh at least 33 kg to be administered the trametinib tablets.
- Patients should be encouraged to take dabrafenib at approximately 12 hour intervals and at similar times each day.
- Study treatment should be administered under fasting conditions, at least 1 hour before or 2 hours after a meal.
- If it is not possible for a patient to tolerate the fasting conditions noted above, study treatment may be administered with a small non-fat meal (e.g. small amount of apple juice/sauce, a piece of dry toast). Patients and their guardians should be advised to avoid administering study drug with milk or high-fat, high-calorie foods.
- Patients who are being breastfed may continue to be breastfed on demand. If the patient is breastfed during collection of PK samples the time of breastfeeding should be recorded as a meal.

- If a patient vomits after taking study drug, the patient should be instructed not to retake the dose and wait for the next scheduled dose.

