## 6.3.1.10 Dose modification and management guideline for skin rash

Guidelines for dose modification and management of skin rash considered to be related to study treatment by the investigator are provided in Table 6-24.

Table 6-24 Mandatory dose modifications and recommended clinical management guidelines for rash

| Rash Events (NCI-CTCAE v                       | ement guidelines for rash   |  |  |  |  |  |  |  |
|--|---|--|--|--|--|--|--|--|
| Grade  | Recommended adverse event management guidelines   | Mandatory dose modification requirements   |  |  |  |  |  |  |
| Grade 1: Rash covering < 10% body surface area | 
 
Initiate prophylactic and symptomatic treatment measures.
 
Consider use of topical corticosteroids or urea containing creams in combination with oral antipruritics or moderate strength topical steroid (hydrocortisone 2.5% cream or fluticasone propionate 0.5% cream)
 
Reassess after 2 weeks
 
 | Continue dabrafenib and trametinib at the same dose.   |  |  |  |  |  |  |
| Grade 2: 10-30% of body surface area           | 
 
If tolerable, as per Grade 1
 
If intolerable, initiate systemic steroids (0.5 to 1 mg/kg/day prednisone or equivalents)
 
If symptoms persist or recur consider skin biopsy.
 
   | If tolerable, continue dabrafenib and trametinib at the same dose.      If intolerable:     1st occurrence      Interrupt dabrafenib and trametinib until ≤ Grade 1, and reduce dabrafenib and trametinib to the next dose level. Re-escalation of the patient's dose is recommended if criteria in Section 6.3.1 are met.   |  |  |  |  |  |  |
| Grade 3: More than 30% of body surface area    | 
 
Obtain a skin biopsy and dermatology consult.
 
Initiate therapy with high dose steroids (1 to 2 mg/kg/day prednisone or equivalents)
 
  | 1st occurrence Interrupt dabrafenib and trametinib until ≤ Grade 1, and reduce dabrafenib and trametinib to the next dose level. Re-escalation of the patient's dose is recommended if criteria in Section 6.3.1 are met.  2nd occurrence Interrupt dabrafenib and trametinib until ≤ Grade 1 or baseline. Once recovered, reduce dabrafenib and trametinib to the next dose level. Re-escalation of the |  |  |  |  |  |  |

Permanently discontinue dabrafenib and trametinib.

Grade 4: Life-threatening

| Rash Events (NC | -CTCAE v4.03)                                      |  |
|-----------------|--|--|

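### Table 6-18 gives steroid doses not scaled to weight (dexamethasone 24 mg/day, methylprednisolone 125 mg) for Grade 3 pneumonitis in a trial that enrols children from 7 kg

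*Protocol*

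**What the plan says.** Section 6.3.1.3, Table 6-18, covers pneumonitis. For Grade 3 the recommended-management column starts with the intravenous step: "Treat with intravenous steroids (methylprednisolone 125 mg or equivalent) as indicated. When symptoms improve to ≤ Grade 1". It then gives the oral step: "a high dose oral steroid (prednisone 1 to 2 mg/kg/day or dexamethasone 4 mg every 4 hours or equivalent". The Grade 4 row refers back to Grade 3.

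The Grade 2 row of the same table states the steroid by weight only: "systemic corticosteroids at a dose of 1 to 2 mg/kg/day prednisone or equivalent as clinically indicated". Table 6-24 does the same for Grade 3 rash: "Initiate therapy with high dose steroids (1 to 2 mg/kg/day prednisone or equivalents".

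On who may be treated, Section 5.2 says "Patients under 6 years old must weigh at least 7 kg at the time of enrollment", and children over 6 must weigh at least 10 kg. Section 6.1.1.1 plans for small children on the combination: "Patients less than 12 years of age who weigh less than 16 kg must be administered the dabrafenib dispersible tablets for oral suspension". Table 6-5 has trametinib bands of 7 to 9.9 kg and 10 to 12.5 kg, and the last band of Table 6-6 is above 72 kg.

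**The concern.** Two options offered side by side should suit the same patient. Here one follows body weight and the other does not, and the cell has no cap, weight limit or pediatric qualifier. The methylprednisolone dose in the same cell is also a single figure for all weights.

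Pneumonitis is an adverse event of special interest (Section 8.1.3), and Grade 3 means severe, oxygen-requiring disease. At stake is a small child who receives the listed dexamethasone or methylprednisolone dose unscaled. No endpoint, sample size, error rate or study-drug dose is involved.

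**Working it through.** **Inputs**
- Dexamethasone 4 mg every 4 hours, with no weight term; prednisone 1 to 2 mg/kg/day; methylprednisolone 125 mg (all Table 6-18, Grade 3).
- Minimum weight 7 kg under 6 years and 10 kg over 6 years (Section 5.2).
- Weight bands from 7 kg (Table 6-5) to above 72 kg (Table 6-6).
- Potency ratio r, in mg prednisone per mg dexamethasone. The protocol gives none. I use r = 1 (milligram for milligram, no potency difference) and an assumed range of 4 to 10.

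**Daily dose.** 4 mg × (24 h / 4 h) = 24 mg/day. The protocol prints no daily total to compare with this.

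**Span of weight that a fixed dose can serve.** Let D = 24 × r be the prednisone-equivalent daily dose and w the weight. The dose lies in the range when 1 ≤ D/w ≤ 2, that is, when D/2 ≤ w ≤ D. The ends differ by a factor of 2 whatever r is. The dosing tables span at least 72/7 = 10.3-fold. So the fixed dose cannot match the prednisone range across this population, and no outside figure is needed to show it.

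**Milligram for milligram.** 24/w > 2 when w < 12 kg. At 7 kg the top of the prednisone range is 2 × 7 = 14 mg/day, and 24/14 = 1.7. At 10 kg it is 24/20 = 1.2.

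**With an assumed potency ratio.** Prednisone-equivalent in mg/kg/day = 24 × r / w:

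| Weight | r = 1 | r = 4 | r = 10 |
|---|---|---|---|
| 7 kg | 3.4 | 13.7 | 34.3 |
| 10 kg | 2.4 | 9.6 | 24.0 |
| 20 kg | 1.2 | 4.8 | 12.0 |
| 33 kg | 0.7 | 2.9 | 7.3 |
| 70 kg | 0.3 | 1.4 | 3.4 |
| Weights within 1 to 2 mg/kg/day | 12–24 kg | 48–96 kg | 120–240 kg |

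**Methylprednisolone.** 125/7 = 17.9 mg/kg, 125/10 = 12.5, 125/20 = 6.25 and 125/50 = 2.5. The cell gives no mg/kg companion for this drug, so no excess can be computed. What can be shown is that the dose is unscaled.

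**Other systemic steroid doses in the protocol**
- Grade 2 pneumonitis: mg/kg.
- Rash, Table 6-24: mg/kg at Grades 2 and 3.
- Pyrexia, Table 6-16: prednisone 10 mg, with a pediatric qualifier.
- Carboplatin pre-treatment, Section 6.3.1.16.5: mg/kg.

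The Grade 3 pneumonitis cell is the exception.

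**The case against.** The case for leaving the text alone has weight. It sits in the recommended column, not the mandatory one. The row calls for a pulmonologist, weight-based prednisone comes first, and Section 6.3.1 tells investigators to use clinical judgment. The oral step applies only after improvement to Grade 1 or less. Harm from dexamethasone therefore needs a small child with Grade 3 or 4 disease who has improved, prednisone passed over, and the full dose given despite specialist input. The protocol gives neither a weight distribution nor a pneumonitis rate. All of this stands and limits the importance of the point. It does not make an unscaled dose suitable for a 7 kg child.

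The closing allowance for equivalents could also be said to permit adjustment. It admits other agents, but it does not correct a listed dose that is itself unscaled.

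A reader might infer more than the text supports:
- **That the protocol declares the two oral doses equal.** It lists them as alternatives. The allowance for equivalents may only admit further drugs.
- **That 2 mg/kg/day is a limit being breached.** It is the top of one option's range. Carboplatin pre-treatment gives prednisone 1 mg/kg every 6 hours for 3 to 4 doses, up to 4 mg/kg in total, though as a brief and different use.

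**Conclusion.** The point holds as a minor safety-text correction in non-binding guidance. Two steroid doses in the Grade 3 cell, which the Grade 4 row refers to, are not scaled to weight in a trial open to children from 7 kg.

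The mismatch with the prednisone range rests on the protocol alone: a two-fold window against a more than ten-fold weight span. Milligram for milligram, the excess over 2 mg/kg/day arises only below 12 kg and is 1.7 times at 7 kg, the edge of eligibility. A reader might infer a far larger overdose, such as 13.7/2 = 6.9 to 34.3/2 = 17.1 times at 7 kg. Those multiples rest wholly on the assumed ratio of 4 to 10, which the documents do not supply.

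A reader might also infer that the cell leaves the steroid-refractory child without direction. The oral step follows improvement to Grade 1 or less ("Grade 1: Radiographic changes only- Asymptomatic"), while the prompt for other immunosuppression begins "If IV steroids followed by high dose oral steroids does not reduce initial symptoms within 48 to 72 hours". That is a literal reading of one compressed sentence. The pulmonologist consultation still applies, as does the mandatory rule to stop trametinib permanently without recovery within 4 weeks. When to escalate is a clinical choice that the protocol gives no basis for settling here, so it forms no part of this conclusion.

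**What to change.** In the Grade 3 recommended cell of Table 6-18:
- State the oral steroid as prednisone 1 to 2 mg/kg/day or equivalent, matching the Grade 2 row. Delete the fixed dexamethasone dose or replace it with a weight-based one.
- Add a pediatric-equivalent qualifier to methylprednisolone 125 mg, as Table 6-16 does for prednisone 10 mg, or give a mg/kg dose.

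Both drugs should be changed together, since correcting dexamethasone alone would leave an unscaled dose first in the sequence. The cost is rewording one table cell, with no extra patients, visits or procedures and no change to any analysis.
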